8.2 Informed consent

Following the recruitment of schools, information sheets will be posted to parents, asking them to return a form to opt them out of participation if they do not want their child to take part. Informed consent or assent will be obtained from all participants who agree to take part in the trial (consent from adults and assent from children). At the beginning of data collections, it will be made clear that student participation is optional. Each school participating in the trial will be asked to identify a named individual who can provide support to any students who become upset or distressed. Any member of the research team and all fieldworkers visiting a school will be required to have a Disclosure and Barring check. All work will be carried out in accordance with General Data Protection Regulation 2018 and the UK Data Protection legislation 2018.

Student information sheets will be provided to schools to distribute to students 1-2 weeks before the baseline data collection. At the baseline data collection, students will be asked to read the information sheet and provide written assent. Time will be allocated at the baseline data collection for students to read the information sheet and ask questions before being asked to sign the Assent Form. Assent will be taken by a member of the research team or a field worker. Completed assent forms will be collected and kept at the recruiting centre (University of Bristol for West of England schools; CTR Cardiff for South Wales schools). Participants will be able to keep the information sheet which will provide details of who to contact if they require further information or support on their or others drug use. The right of the participant to refuse to participate without giving reasons, or whose parents/carers opt them out of the trial will be respected. For those students who opted out/declined to participate alternative arrangements will be provided to allow them to remain in the data collection environment to avoid embarrassment.

8.3 Randomisation

Randomisation will be completed at school-level. Randomisation will be coordinated centrally by the CTR. The randomisation schedule will be stratified and will be prepared and held by an independent statistician within the CTR. Within each of the two countries, schools will be organised into the two FSM strata. Each school will be assigned an ID number, after which an independent statistician will randomly allocate schools within each stratum to one of two arms using random block allocations. Block sizes of 2, 4 and 6 will be used. Further detail on this will be included in the unblinded randomisation protocol.

9 Withdrawal & losses to follow-up

9.1 Withdrawal

Schools and participants will have the right to withdraw consent for participation in any aspect of the FRANK friends study at any time. Participants' care from any services will not be affected at any time by declining to participate or withdrawing from the trial. If a participant initially consents but subsequently withdraws from the trial, a clear distinction will be made as to what aspect of the trial the participant is withdrawing from. Whilst it is possible to withdraw any data collected as part of the research it is only possible for peer supporters to withdraw from attending training to be a FRANK friends peer supporter. As these are informal peer-led interventions, it is not possible for participants to withdraw from receiving the intervention as this would require no contact with any trained peer supporters. In all instances, schools and participants who consent and subsequently withdraw should complete a withdrawal form or the withdrawal form should be completed on the participant's behalf by the Cardiff or Bristol Trial Manager(s) based on information provided by the participant. Withdrawal forms from West of England schools should be sent to the Trial Manager(s) and kept in the site file at the University of Bristol. Withdrawals from South Wales schools should be sent to the Trial Manager(s) in the CTR. Any queries relating to potential withdrawal of a school or participant should be forwarded to the Trial Manager(s) immediately.

9.2 Lost to follow-up

The outcome measurements will be assessed at two time points. Baseline measures will be assessed prior to randomisation of schools into the two trial arms (control and intervention conditions, 24 schools [clusters] in each, see section 13.3, sample size). A second set of measurements will take place 24-months post randomisation as per the baseline protocol. Following the protocols used in previous trials multiple absentee sessions to minimise

attrition will be carried out. (24) All schools, whether intervention of control will be incentivised to remain in the trial by offering a payment of £1000 at the end of the trial.

10 Trial Intervention

10.1 The FRANK friends intervention

FRANK friends is a peer-led drug prevention intervention to prevent drug use in UK year 9 secondary school children. FRANK friends has been developed over a 31-month NIHR PHR funded study (PHR - 12/3060/03) comprising intervention development, prototyping and a pilot cRCT.

Based on diffusion of innovations theory,(30) FRANK friends aims to diffuse information from www.talktofrank.com via secondary school students' social networks in UK Year 9 (aged 13-14). Following methods developed in the ASSIST intervention and found to be acceptable in the pilot study, FRANK friends has five stages:

- Nomination of peer supporters: Students in UK year 9 are asked to identify influential peers using three questions, "Who do you respect in year 9 at your school?", "Who are good leaders in sports or other groups activities in year 9 at your school?", and "Who do you look up to in year 9 at your school?" The 17.5% of Year 9 students receiving the most peer nominations are invited to a recruitment meeting;
- Recruitment of peer supporters: A meeting is held with nominees to explain the role of a peer supporter and answer questions. Parental consent is sought for participation in a training course;
- 3. Training of peer supporters: A 2-day training course is held out of school, facilitated by an intervention delivery team. Trainers are typically experienced in youth work and/ or health-promotion and employed by the NHS, third-sector charities, or local government. Trainers provide information on the effects and risks associated with specific drugs, minimising potential harms, and the law from Talk to FRANK. Peer supporters practise communication skills including, listening, negotiation, how to talk with their peer group about drugs, and how to access www.talktofrank.com by computer or smartphone. Methods used to achieve these aims include participatory learning activities such as role plays, student-led research, small group work and discussion, and games;
- 4. Intervention period: Peer supporters are asked to have informal conversations with their peers on drugs, when travelling to and from school, in breaks, at lunchtime, and after school in their free time, and log a record of these conversations in a pro-forma diary. Over the 10-week period four follow-up school visits are made by intervention

delivery staff to meet with peer supporters to provide support, trouble shooting, and monitor peer supporters' diaries;

5. Acknowledgment of peer supporters' contribution: At the end of the intervention peer supporters receive a certificate.

All staff who train FRANK friends peer supporters will receive two days training by members of the research team who trained staff in the pilot. Training protocols are based on those used in the ASSIST 'train the trainer' model. (31)

In England, funding for FRANK friends intervention delivery staff will come from the NIHRs West of England Clinical Research Network (CRN) and commissioners in local government. FRANK friends will be delivered in England by the West of England CRN staff. In Wales, funding for intervention delivery will come from Public Health Wales (PHW), based in the NHS, and be delivered by existing staff who work in smoking prevention.

The comparison schools will continue with usual practice which may or may not involve drug education. The details of any drug education, including other relevant interventions, will be examined as part of the process evaluation (see section 15).

11 Trial procedures

The outcome measurements will be assessed at two time points. Baseline measures will be assessed prior to randomisation of schools into the two trial arms (control and intervention conditions, 24 schools [clusters] in each, see section 13.3, sample size). A second set of measurements will take place 24-months post randomisation as per the baseline protocol.

11.1 Data collections

Students will be in UK year 9 (aged 13-14 years) at baseline and complete paper self-report questionnaires under 'exam conditions' in a classroom or school hall. School staff will be asked to be present but not help students to ensure anonymity. Fieldworkers will be on hand to provide support to students who require help. Completed paper questionnaires will be transported to CTR by the Trial Manager(s) or couriered. Data from questionnaires will be stored in anonymised form, using participant identification numbers. Participant identification numbers and corresponding participant names will be held in separate files. Both files will be stored in secure password protected folders.

12 Safety reporting

Definitions

Term	Definition	
Adverse Event (AE)	Any untoward medical occurrence in a participant or clinical trial	
	participant administered a medicinal product/ intervention and	
	which are not necessarily caused by or related to that product	
Serious Adverse Event	Any adverse event that -	
(SAE)	Results in death	
	 Is life-threatening* 	
	 Required hospitalisation or prolongation of existing 	
	hospitalisation**	
	Results in persistent or significant disability or incapacity	
	Consists of a congenital anomaly or birth defect	
	Other medically important condition***	

*Note: The term 'life-threatening' in the definition of serious refers to an event in which the trial participant was at risk of death at the time of the event; it does not refer to an event which hypothetically might have caused death if it were more severe.

** **Note:** Hospitalisation is defined as an inpatient admission, regardless of the length of stay, even if the hospitalisation is a precautionary measure for continued observation. Pre-planned hospitalisation (e.g. for pre-existing conditions which have not worsened, or elective procedures) do not constitute an SAE.

*** **Note:** other events that may not result in death, are not life-threatening, or do not require hospitalisation, may be considered as an SAE when, judged by the Chief Investigator to jeopardise the participant and may require medical, psychological or surgical intervention to prevent one of the outcomes listed above. Examples within this trial, may include a young person revealing incidences of self-harm, sexual abuse, and grooming by being provided drugs.

No adverse events arising from the intervention are expected. All intervention materials will be based on information from www.talktofrank.com and as a result are in line with the current, widely publicised UK governmental guidelines. CTR standard operating procedures for managing and reporting any serious adverse events (SAE) will be followed, which reflect those outlined in Good Clinical Practice (GCP) guidance. Adverse events which do not fall into the GCP categories of an SAE are defined as non-serious and will not be collected. The chief investigator will review SAEs examining the link with the intervention and sign all SAE reports. Once an SAE is received at the CTR, it will be sent to the Chief Investigator (or their delegate) for an assessment of expectedness. Only reports of related and unexpected Serious Adverse

Events (SAEs) should be submitted to the REC and TSC. These should be sent within 15 days of the chief investigator becoming aware of the event. If the chief investigator deems the SAE to be related to the intervention they will be reported to the sponsor (Cardiff University) within 24 hours of the trial team becoming aware of an event. In the pilot study no problems with the FRANK friends intervention or, questionnaires, were encountered in the pilot study, and there were not any AEs or SAEs reported.

Expected AE/SAE: There are no expected AE's/SAE's. Any planned treatments received by participants at the start of the trial will not be considered as AE's/SAE's.

Related AE/SAE: There are no AE's/SAE's expected to be related specifically to the trial interventions. The Chief Investigator (or delegate) will however make an assessment of causality in relation to the intervention for all SAEs reported according to the SAE working guidance document.

Trial Specific SAE Reporting requirements

For the purposes of this trial the following events will also be considered SAEs and must be captured on the SAE form and reported to the CTR with 24 hours of knowledge of the event:

- incidences of self-harm;
- sexual abuse;
- grooming by being provided drugs.

For the purposes of this trial the following events will not require reporting as SAEs:

• Any planned treatments received by participants at the start of the trial.

12.1 Reporting procedures

The CI (or delegate from the trial team) should sign and date the SAE reports to acknowledge that he/she has performed the seriousness and causality assessments. A completed SAE form for all events requiring immediate reporting should be submitted via email or phone to the CTR within 24 hours of knowledge of the event (see box below for email address and telephone number). A separate form must be used to report each event, irrespective of whether or not the events had the same date of onset. The participant will be identified only by their participant identifying number, partial date of birth (mm/yy) and initials. The participant's name should not be used on any correspondence. It is also required that sites respond to and clarify any queries raised on any reported SAEs and report any additional information as and when it becomes available through to the resolution of the event.

Additionally, the CTR may request additional information relating to any SAEs and the site should provide as much information as is available to them in order to resolve these queries.

An SAE form is not considered as complete unless the following details are provided:

- Full participant trial number
- Details of the Adverse Event
- A completed assessment of the seriousness, and causality as performed by the CI (or another on the delegation log).

If any of these details are missing, the school/individual will be contacted and the information should be provided by the school/individual to the CTR within 24 hours.

Serious Adverse Event (SAE) email address:

[contact]

SAE Telephone number:

[name] ([name])

Serious adverse events should be reported from time of signature of informed consent until the end of the 24-month follow-up has been completed.

13 Statistical considerations

13.1 Randomisation

Clusters (schools) will be randomised in a 1:1 ratio to receive either the 10-week FRANK friends intervention in addition to usual practice or usual practice. Within each trial area (the West of England and South Wales), schools will be stratified on the percentage of students in receipt of FSM to ensure balance across arms on parental socioeconomic disadvantage. Randomisation of the schools will occur after all schools have been recruited and they will be informed of their allocation after baseline data have been collected. All schools will be assigned an ID number, after which an independent CTR statistician, will randomly allocate recruited schools to Intervention or Control using computer generated random number block allocations. The independent CTU statistician will allocate Intervention or Usual practice to

ID numbers and inform the designated intervention delivery team member in each area so that delivery of intervention can start as soon as a school's baseline data collection has been completed. Schools in both arms will continue with their usual educational activities with regards to drugs education.

13.2 Blinding

All parties will be blind to allocation during the baseline data collection. It is not possible for FRANK friends study participants (students), teachers, trial managers, the intervention delivery team or researchers involved in the process evaluation to be blind to intervention status. However, fieldworkers at outcome data collections will remain blind to intervention status as will the statistician analysing the primary and secondary outcome data and the health economists undertaking the economic analysis. If school allocation becomes apparent during interactions with schools we will record this. Potential risks of the intervention to participants are minimal but in the case where unblinding is necessary, the allocation schedule will be available to the researchers either electronically via the independent CTR statistician's copy.

13.3 Sample size

The latest population-level prevalence study from the 2016 SDDU survey indicates the lifetime prevalence of drug use at the 24-month follow-up (among 15 year olds) will be 37%.(3) This is a 13% increase from the previous survey in 2014.(4) There is some uncertainty around this estimate as it is not in line with other comparable surveys (lifetime prevalence in 15 year olds in 2015 SALSUS was 19%).(5) Table 1 shows the required sample size based on prevalence in the usual practice group ranging between 19% and 37%. A 25% relative reduction in prevalence approximates to the pooled odds ratio of 0.70 for cannabis use found in a systematic review peer-led drug prevention programs (19) and the effect of FRANK friends compared with usual practice found in the pilot cRCT,(31) demonstrating that such an effect size is plausible and consistent with effect sizes seen in the literature. The potential population level reach of the intervention, coupled with the ability to repeat delivery every year, suggests that a reduction of this magnitude would be of public health importance.

The trial will take account of clustering. In the pilot cRCT the intracluster correlation (ICC) for the comparison between FRANK friends and usual practice was 0.003 at the 18-month

follow-up. Assuming 122 students per school, an ICC of 0.01 (to be conservative), coefficient of variation of sample size of 0.28, and 13.7% rate of attrition (based on the pilot data plus 1 additional school in case of drop out) if we use the 2014 prevalence rate of 24%, a trial involving 48 schools would provide 90% power at a 5% significance level (Table 1). Using the 2016 SDDU prevalence rate of 37% in usual practice, 36 schools is required. To ensure we are adequately powered, we propose to recruit 48 schools, as 88% power can be achieved if we find the 2016 SDDU prevalence rate and the ICC is larger at 0.02. If prevalence is closer to the SALUS rate of 19%,(5) we will have 84% power based on a ICC of 0.01. Applying the parameters from the pilot cRCT, a trial involving 48 schools would also provide 88% power to detect a difference of 12.0% vs. 8.7% in the secondary outcome of monthly drug use by 15 years of age.

Table 1. Sample size calculations (number of schools) to detect a difference in lifetime illicitdrug use at 15 years of age ^a (bold figures indicate variations in parameters with mainsample size calculation at top)

Power	Effect size ^a	Prevalence ^b	ICC °	N schools ^d	N students
90	24.0 vs. 18.1%	24.0%	0.01	48 (24 intervention)	5655
90	37.0 vs. 29.1%	37.0%	0.01	36 (18 intervention)	4242
90	19.0 vs. 14.1%	19.0%	0.01	56 (28 intervention)	6786
88	37.0 vs. 29.1%	37.0%	0.02	48 (24 intervention)	5655
90	24.0 vs. 18.1% ^a	24.0%	0.003	32 (16 intervention)	3676

^a Based on OR from FRANK friends vs. usual practice in pilot cRCT(31) and MacArthur meta-analysis of peer-led drug prevention interventions.(19) ^b Smoking drinking and drug use study among young people in England: lifetime illicit drug use prevalence age 15 in 2014 (4) 2016 (3); 2015 Scottish Schools Adolescent Lifestyle and Substance Use Survey (SALSUS).(5) ^c ICC from model comparing FRANK friends vs. usual practice in pilot cRCT(31); ^d Inflated for 13.7% student dropout (based on pilot cRCT) (31) plus one extra 1 school.

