14.1 Main analysis

A detailed statistical analysis plan will be written prior to analysis. The reporting of findings will be in accordance with the CONSORT guidelines for cluster RCTs (29) and SPIRIT recommendations for reporting trials of interventions.(32) Statistical analysis will be performed in R or Stata (version 13 or higher).

All analyses will be intention to treat (i.e. students will be analyzed in the groups to which they were randomised, regardless of adherence to the intervention) and missing outcome data will not be replaced. Statistical tests and confidence intervals (CI) will be two-sided. Between-group comparisons will be presented with 95% confidence intervals wherever possible. As the trial includes a reasonable number of clusters, the analysis will be based on the individual student, allowing for clustering between students within school using robust standard errors. All analyses will control for baseline outcomes (if applicable), school level stratification variables (proportion of children eligible for FSM: country-specific median, geographical area) and student characteristics (age, gender, parental employment status).

Primary outcome: Multilevel logistic regression models will be used to compare the lifetime use of illicit drugs at 24 months by arm, and results presented as odds ratios and 95% CIs. Intra-cluster correlations (ICCs) alongside 95% CIs will also be reported.

Secondary outcomes: Multilevel linear (continuous outcomes) and logistic (binary outcomes) regression models will be used to compare secondary outcomes.

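### The 90% and 84% powers credited to 48 schools are those of 40 schools with 122 analysed students each; 48 schools have more, and the 88% at ICC 0.02 needs rechecking

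*Protocol*

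**What the plan says.** Protocol section 13.3 sets its inputs in one sentence: "Assuming 122 students per school, an ICC of 0.01 (to be conservative", a coefficient of variation of cluster size of 0.28, and 13.7% attrition plus one spare school. From these it concludes that "a trial involving 48 schools would provide 90% power at a 5% significance level" when usual-practice prevalence is 24%. Two robustness statements follow for the same 48 schools. At the Scottish survey's prevalence of 19%, "we will have 84% power based on a ICC of 0.01". And "88% power can be achieved if we find the 2016 SDDU prevalence rate and the ICC is larger at 0.02". A further 88% is given for monthly use (12.0 vs 8.7%), using pilot parameters.

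Table 1 sets the 90% and the ICC 0.02 figure of 88% beside 48 schools and 5655 students. Its footnote d describes the number of schools as "Inflated for 13.7% student dropout (based on pilot cRCT") with one school added. Section 13.1 fixes 1:1 allocation by school, and section 14.1 says "Statistical tests and confidence intervals (CI) will be two-sided". The section names no power formula or software, and does not say whether 122 is a count of enrolled or of analysed students.

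**The concern.** Attrition of individual students makes each school's analysed group smaller. The number of schools stays the same unless a school itself withdraws. Section 13.3 handles student loss by dividing the school count by 0.863, then reports power as if the pre-inflation design were the trial being run. In a cluster trial the two are not equivalent: for the same number of analysed students, more and smaller clusters carry more information.

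These powers are the reason given for choosing 48 schools and for believing that the trial can withstand a lower prevalence or a higher ICC. If they belong to another design, the steering committee cannot read from them how much room there is for school loss, heavier attrition or stronger clustering. If one of them also fails to fit the basis of the others, the scenarios cannot be compared with one another.

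**Working it through.** **Inputs.** From section 13.3: m = 122, CV = 0.28, ICC = 0.01 or 0.02, attrition 13.7%, and the prevalence pairs in Table 1. From sections 13.1 and 14.1: equal allocation and two-sided tests at 5%. Assumptions: CV is unchanged by dropout, and ICC is 0.003 (the pilot value) for monthly use.

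**Formulae**, for k schools with m analysed in each:
- Design effect D = 1 + ((1 + CV²)m − 1) × ICC
- SE² = [p1(1 − p1) + p2(1 − p2)] × D / (km/2)
- λ = (p1 − p2)/SE. Power comes from the noncentral t distribution with k − 2 df.

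**Step 1: reproduce the 90%.** Take k = 40, m = 122.
- D = 1 + (1.0784 × 122 − 1) × 0.01 = 2.306
- Students per arm = 20 × 122 = 2440
- SE² = (0.1824 + 0.1482) × 2.306 / 2440, so SE = 0.01768
- λ = 0.059 / 0.01768 = 3.34. With 38 df, power = 90.2%.

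**Step 2: confirm the basis from the student totals.** The smallest even k that reaches 90% (rounded) by this method, multiplied by 122/0.863 and rounded up, is:
- 24%, ICC 0.01: k = 40, giving 5655
- 37%, ICC 0.01: k = 30, giving 4242
- 19%, ICC 0.01: k = 48, giving 6786
- 24%, ICC 0.003: k = 26, giving 3676

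These are the four distinct student totals in Table 1. For the main row, 40/0.863 + 1 = 47.3, hence 48 schools. The pooled normal formula reaches 90% at 38 schools in the main row, giving 5372 students, so it is probably not what was used.

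**Step 3: cluster size after dropout.** Two readings are possible.
- 5655 enrolled: 5655/48 = 117.8 per school, × 0.863 = 101.7 analysed.
- 122 enrolled per school: 122 × 0.863 = 105.3 analysed, but 48 × 122 = 5856, which is not the planned 5655.

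**Step 4: power of the 48-school trial.** With m = 101.7 the number analysed per arm is again about 2440 (24 × 101.7). The design effect, however, falls to 1 + (1.0784 × 101.7 − 1) × 0.01 = 2.086, so λ = 3.51 and power with 46 df is 93.0%.

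| Scenario | Stated | 40 x 122, t | 40 x 122, pooled normal | 48 schools, t (101.7 to 105.3) | 48 schools, pooled normal |
|---|---|---|---|---|---|
| 24.0 vs 18.1%, ICC 0.01 | 90% | 90.2% | 91.5% | 93.0-93.4% | 93.9-94.2% |
| 19.0 vs 14.1%, ICC 0.01 | 84% | 84.2% | 85.9% | 87.9-88.4% | 89.1-89.6% |
| 37.0 vs 29.1%, ICC 0.02 | 88% | 85.5% | 87.1% | 89.9-90.2% | 91.0-91.2% |
| 12.0 vs 8.7%, ICC 0.003 (assumed) | 88% | 87.9% | 89.4% | about 90% | about 91% |

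**Step 5: one school lost.** With 47 schools the t powers in the first three rows are 92.5-92.9%, 87.2-87.7% and 89.3-89.6%, less than one point lower.

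**The case against.** The strongest defence is that nothing is concealed. Footnote d says openly that the school count is inflated for dropout, and powering an analysed sample before inflating recruitment is common practice. Read that way, the quoted power is a design target for the sample left after losses, and replacing lost students with extra schools is a cautious choice. The direction of the error is also safe: every recomputed power for 48 schools exceeds the stated one. All of this stands, and it limits the point to one of reporting. It does not rescue the wording, because section 13.3 attaches the 90% to a trial of 48 schools and nowhere mentions 40.

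A second objection concerns the 88% at ICC 0.02. The protocol names no method, and by normal approximation 40 x 122 gives about 87%, as does the t calculation with equal cluster sizes (87.3%). A reader might infer that the figure is plainly wrong or cannot be reproduced. The documents do not support that: the gap is 2.5 points by t and about one point otherwise. What remains is narrower. The t method, which returns the 90%, the 84% and the student totals, does not return this 88%, and none of the methods tried rounds to it on 40 x 122.

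Third, taking 105.3 analysed per school as the only correct basis would conflict with the planned 5655, so both readings are carried here.

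**Conclusion.** The stated 90% and 84% are the powers of 40 schools with 122 analysed students each, not of the 48-school trial to which section 13.3 attributes them. On the protocol's own inputs, 48 schools have about 93-94% and 88-90%, so the figures are understated by about 3 to 4 points and 4 to 6 points. The 88% at 37% prevalence and ICC 0.02 should be rechecked, since it lies between the 40 x 122 value (85.5% by t, about 87% by normal approximation) and the 48-school value (about 90-91%). The other 88%, for monthly use, fits 40 x 122 at 87.9% if the pilot ICC of 0.003 applies.

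A reader might infer that the trial is underpowered or that 48 is the wrong number of schools. Neither follows: the mislabelling is conservative, and the recruitment target is sufficient on the protocol's own assumptions.

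The identification of the 40 x 122 basis is firm, because it rests on two powers and four student totals. The exact 48-school values depend on the method (about one point), on whether 122 is enrolled or analysed (about half a point), and on an unchanged CV.

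**What to change.** Correct the text of section 13.3 and Table 1; the 48 schools do not change.

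- Name one power method and use it for every scenario.
- Say whether 122 is enrolled or analysed, so that power and the planned 5655 rest on the same count.
- Apply the 13.7% attrition to cluster size, and school loss to the number of schools.
- Restate the 48-school powers. By t, with 101.7 to 105.3 analysed per school, these are about 93% (24%), 88% (19%) and 90% (37%, ICC 0.02), each less than one point lower if a school is lost.
- Put the monthly-use power on the same basis (about 90%) and state the ICC used.

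The lighter alternative is to keep the present figures, label them as the powers of 40 schools with 122 analysed each before inflation, and correct the ICC 0.02 row to that basis. Either way the cost is a short recalculation and a wording change, with no effect on recruitment, conduct or analysis.
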